8.1.2. Subject Exclusion Criteria

Criteria with exclusionary laboratory values are to be based on the most recent laboratory result available prior to randomization.

1. Current or history of significant alcohol consumption for a period of more than 3 consecutive months within 1 year before Screening (significant alcohol consumption is defined as more than 2 units/day for females and more than 4 units/day for males, on average).
2. Prior (at any point) or planned (during the study period) ileal resection, or prior (within 5 years before Screening) or planned (during the study period) bariatric surgery (eg, gastric bands, gastroplasty, roux-en-Y gastric bypass).
3. HbA1c $> 9.5\%$ within 60 days before Day 1.

4. Evidence of other forms of known chronic liver disease including:
 - Positive test result at Screening for hepatitis B surface antigen (HBsAg)
 - Active hepatitis C virus (HCV) infection (positive for HCV ribonucleic acid [RNA] at Screening) or history of positive HCV RNA test result
 - PBC, PSC, autoimmune hepatitis, or overlap syndrome
 - Alcoholic liver disease
 - Wilson's disease, hemochromatosis, or iron overload
 - Alpha-1-antitrypsin (A1AT) deficiency as defined by diagnostic features in liver histology (confirmed by A1AT level below the lower limit of normal [LLN] or exclusion at the Investigator's discretion)
 - Prior known drug-induced liver injury within 5 years before Day 1
 - Known or suspected ██████████
 - History of liver transplant, current placement on a liver transplant list, or MELD score >12.
5. Histological presence of cirrhosis.
6. Total bilirubin >1.5 mg/dL (subjects with Gilbert's syndrome may be enrolled despite a total bilirubin level >1.5 mg/dL if their conjugated bilirubin is <1.5× ULN).
7. Conjugated bilirubin ≥1.5 x ULN.
8. AST or ALT ≥10× ULN, international normalized ratio (INR) ≥1.4, or serum creatinine ≥1.5 mg/dL.
9. Creatine phosphokinase >5x ULN.
10. Platelet count <100 000/mm³.
11. LDL ≥190 mg/dL and already on a stable dose of statin and/or proprotein convertase subtilisin/kexin type 9 (PCSK9) inhibitor for ≥30 days at Screening.
12. Inability to safely undergo a liver biopsy.
13. History of biliary diversion.
14. Known positivity for human immunodeficiency virus infection.
15. Subjects with recent history (within 1 year of Day 1) of significant atherosclerotic cardiovascular disease (myocardial infarction, unstable angina, acute coronary syndrome, cerebrovascular accident [stroke], cerebrovascular ischemia, transient ischemic attack, or peripheral vascular disease requiring intervention). Such subjects may be identified by different means, including but not limited to, an abnormal ECG, a history or planned cardiovascular intervention such as coronary revascularization (eg, percutaneous coronary intervention or coronary artery bypass graft), coronary angioplasty, stenting, carotid atherectomy, or placement of a cardiac pacemaker or defibrillator.

- Controlled hypertension without other recent manifestations of significant atherosclerotic cardiovascular disease and placement of cardiac pacemaker or defibrillator for reasons other than atherosclerotic cardiovascular disease (eg, for treatment of atrial fibrillation subsequent to nodal ablation) is not exclusionary.
16. Other medical conditions that may diminish life expectancy to <2 years, including known cancers (except carcinomas in situ or other stable, relatively benign carcinomas).
 17. Known substance abuse in the year before Screening.
 18. Pregnancy, planned pregnancy, potential for pregnancy (ie, unwillingness to use effective birth control during the study), or current or planned breast feeding.
 19. Participated in a clinical research study with any investigational product being evaluated for the treatment of diabetes, weight loss, or NASH in the 6 months before Day 1.
 20. Received any investigational product not being evaluated for the treatment of diabetes, weight loss, or NASH from Screening to Day 1, within 30 days before Day 1, or within 5 half-lives of the compound (whichever was longer) before Day 1.
 21. Previous exposure to OCA.
 22. Mental instability or incompetence, such that the validity of informed consent or ability to be compliant with the study, is uncertain.
 23. History of known or suspected clinically significant hypersensitivity to OCA or any of its components.
 24. Any other condition that, in the opinion of the Investigator, would impede compliance or hinder completion of the study.
 25. Acute cholecystitis or acute biliary obstruction.
 26. BMI >45 kg/m² with at least 1 of the following comorbidities:
 - Hypertension with blood pressure $\geq 140/90$ mmHg if <60 years, $\geq 150/90$ mmHg if ≥ 60 years, or on antihypertensive medication
 - Hyperlipidemia defined as LDL cholesterol ≥ 160 mg/dL, total cholesterol ≥ 200 mg/dL, or on lipid lowering medication
 - Type 2 diabetes per 2013 American Diabetes Association criteria

8.2. Subject Withdrawal Criteria

Subjects can be discontinued from investigational product by the Investigator at any time for clinical safety concerns. Subjects who are discontinued from investigational product are expected to continue in the study and should follow the regular visit schedule for the duration of the study. Subjects who permanently discontinue from investigational product are not required to be assessed more frequently than the scheduled study visits provided stabilization of the clinical event has occurred leading to discontinuation (per discretion of the Investigator and upon discussion with the Medical Monitor).

Refer to [Section 7.4](#) and [Section 7.7](#) for withdrawal criteria related to potential hepatic injury and/or decompensation; progression to cirrhosis; treatment-emergent acute or nonacute

pancreatitis; Grade 3 pruritus, AEs \geq Grade 3 in severity and possibly, probably, or definitely related to investigational product; liver transplantation and bariatric surgery. Other reasons, including withdrawal of consent or lost to follow-up, are described in [Section 8.2.1](#) to [Section 8.2.3](#) below.

Bariatric Surgery (Gastric Bypass)

Subjects must discontinue investigational product after undergoing bariatric surgery. A liver biopsy should be obtained at the time of surgery. Subjects should be encouraged to continue study visits, despite stopping investigational product, for continued study data collection but may withdraw consent at any time.

8.2.1. Other Reasons for Discontinuation of Investigational Product

Subjects who discontinue investigational product are expected to continue in the study until the end of the study or at the discretion of the Sponsor. With the exception of liver transplant, if a subject experiences a suspected or confirmed clinical outcomes event, he or she should continue the regular visit schedule and continue taking investigational product as long as the Investigator assesses it as safe. Subjects who discontinue investigational product prior to termination of the study need to also continue to follow the regular visit schedule through to study closure. In general, subjects should be strongly encouraged to both stay on investigational product and remain in the study until study termination. Specific strategies to encourage continued subject participation in the study will be outlined in a Subject Retention Plan. Early termination procedures should only be conducted if the subject withdraws consent (see [Section 9.9.9](#)).

The following events are considered appropriate reasons for a subject to discontinue investigational product; however, these subjects are expected to continue in the study until study termination (or at the discretion of the Sponsor):

- The Investigator or Sponsor considers that it is advisable or in the best interest of the subject.
- The occurrence of clinical or laboratory AEs considered by the Investigator to be clinically important.
- Modification of consent:
 - Consent may be modified to discontinue study visits but allow semi-annual telephone contact of subject, subject's primary care physician, or personal contacts who can provide information on behalf of the subject by the investigator
- Consent may be modified to discontinue study visits or semi-annual telephone contact but allow continued access to medical records to assess for potential major adverse cardiovascular events (MACE) and liver-related clinical outcomes
- Withdrawal of consent:
 - Consent may be fully withdrawn

The Investigator must notify the Medical Monitor as soon as possible when a decision to discontinue a subject from treatment is made or when any subject prematurely withdraws from the study.

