Subjects will be screened for a period of up to 12 weeks before entering the study. Approximately 2370 subjects with NASH who meet all eligibility criteria will be randomized to receive OCA 10 mg, OCA 25 mg, or matching placebo in a 1:1:1 ratio for the duration of the study, in conjunction with local standard of care. Randomization of subjects with fibrosis stage 2 or stage 3 will be stratified by presence of type 2 diabetes at enrollment (yes/no) and use of thiazolidinediones (TZDs)/glitazones or vitamin E at baseline (yes/no). Biopsy-confirmed NASH will be determined by central reading of liver histology at Screening, and all subsequent histology assessments will be performed centrally in a blinded fashion.

Investigational product (ie, OCA or placebo) will be taken orally, with water, once daily. Subject safety and laboratory assessments will be evaluated at clinical visits occurring after the first month and once every 3 months following the initiation of treatment (Day 1) through Month 18. Following the Month 18 visit, clinic visits will occur every 6 months for the remaining duration of the study.

With the exception of liver transplant, if a subject experiences a suspected or confirmed clinical outcomes event, he or she should continue the regular visit schedule and continue taking investigational product as long as the subject has not met any of the criteria for discontinuation outlined in the protocol. Subjects who discontinue investigational product are expected to be followed through to study closure (or at the discretion of the Sponsor). Additional strategies to encourage continued subject participation in the study will be outlined in a Subject Retention Plan.

EOS = end of study

▲ Biopsy (Subjects without a liver biopsy performed within 6 months before Day 1 will have a biopsy at the second Screening Visit).

^a Number of adjudicated events accrued in placebo and OCA 25 mg groups combined.

Concomitant Medications:

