Subjects will be screened for a period of up to 12 weeks before entering the study. Approximately 2370 subjects with NASH who meet all eligibility criteria will be randomized to receive OCA 10 mg, OCA 25 mg, or matching placebo in a 1:1:1 ratio for the duration of the study, in conjunction with local standard of care. Randomization of subjects with fibrosis stage 2 or stage 3 will be stratified by presence of type 2 diabetes at enrollment (yes/no) and use of thiazolidinediones (TZDs)/glitazones or vitamin E at baseline (yes/no). Biopsy-confirmed NASH will be determined by central reading of liver histology at Screening, and all subsequent histology assessments will be performed centrally in a blinded fashion.

Investigational product (ie, OCA or placebo) will be taken orally, with water, once daily. Subject safety and laboratory assessments will be evaluated at clinical visits occurring after the first month and once every 3 months following the initiation of treatment (Day 1) through Month 18. Following the Month 18 visit, clinic visits will occur every 6 months for the remaining duration of the study.

With the exception of liver transplant, if a subject experiences a suspected or confirmed clinical outcomes event, he or she should continue the regular visit schedule and continue taking investigational product as long as the subject has not met any of the criteria for discontinuation outlined in [Section 7.7](#). Subjects who discontinue investigational product are expected to be followed through to study closure (or at the discretion of the Sponsor). Specific strategies to encourage continued subject participation in the study will be outlined in a Subject Retention Plan ([Section 7.9](#)).

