Gastroenteritis (established severe abdominal pain, vomiting, diarrhea) or dehydration	Interrupt	If no evidence of liver injury is detected, IP may be restarted at the same dose after resolution of intercurrent illness.
AE categorized as ≥Grade 4 in severity and not or unlikely related to IP	Interrupt	
Potential renal impairment (serum creatinine exceeds upper threshold criteria [Section 7.6])	Interrupt after confirmation by repeat testing	Subject may be rechallenged after a minimum of 30 days if laboratory results return to within threshold criteria and approved by the Medical Monitor and Investigator.
Symptomatic cholelithiasis and/or cholecystitis	Interrupt	Subjects should remain in the study and complete all protocol-specified assessments, as defined in Table 1 , while off IP. Subjects may resume IP: 
 • After full resolution from a cholecystectomy and after receiving approval from the Investigator and Medical Monitor provided there are no signs or symptoms suggestive of retained or recurrent bile duct stones • If it is deemed, after surgical consultation, that the subject does not need to undergo surgery, symptoms have resolved, and after receiving approval from the Investigator and Medical Monitor.

Table 4: Criteria for Dose Adjustment, Interruption, Discontinuation and Rechallenge (Continued)

DOSE INTERRUPTION		
Criteria	Action Taken with IP^a	Rechallenge^b
Pregnancy	Interrupt	Subject should continue with the study visit schedule. The subject may re-start investigational product when she is no longer pregnant or breastfeeding at the discretion of the Investigator and after discussion with the Medical Monitor as described in Section 15.1.12 .
DOSE DISCONTINUATION		
Criteria	Action Taken with IP	Rechallenge
Potential Hepatic Decompensation ^c or Progression to Child Pugh B or C [CP Score \geq 7]	Discontinue ^g / No Rechallenge	Continue to return for scheduled study visits for safety follow up; however, the subject should not be rechallenged. Monitor closely for clinical outcomes according to protocol assessments.
Treatment-emergent acute or nonacute pancreatitis	Discontinue ^g / No Rechallenge	Continue to return for scheduled study visits for safety follow up; however, the subject should not be rechallenged.
\geq Grade 3 pruritus ^f		
Other AEs \geq Grade 3 considered possibly, probably, or definitely related to IP		
Liver transplantation		
Bariatric Surgery (Gastric Bypass)		

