AE = adverse event; ALP = alkaline phosphatase; ALT = aspartate aminotransferase; CP = Child-Pugh; DILI = drug-induced liver injury; IP = investigational product

^a If subject is unable to be evaluated promptly, study drug must be immediately interrupted.

^b Requires complete documentation of full resolution or normal/baseline based on laboratory parameters and symptoms.

^c ALT, ALP, direct or total bilirubin, or INR.

^d Signs and symptoms of hepatic injury include severe fatigue, nausea, vomiting, right upper quadrant pain, fever, rash, and eosinophilia.

^e Clinically evident complications of portal hypertension (eg, ascites, variceal hemorrhage, hepatic encephalopathy).

^f Severity per the current version of the CTCAE.

^g Subjects who permanently discontinue from investigational product are expected to continue in the study and should follow the regular visit schedule for the duration of the study. The Investigator should use clinical judgement to determine if more frequent assessments of laboratory tests and symptoms are necessary until stabilization of the clinical event leading to discontinuation has occurred (per discretion of the Investigator and upon discussion with the medical monitor).

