Approximately 2480 subjects with NASH who meet all eligibility criteria will be randomized to receive OCA 10 mg, OCA 25 mg, or matching placebo in a 1:1:1 ratio for the duration of the study, in conjunction with local standard of care. Randomization of subjects with fibrosis stage 2 or stage 3 will be stratified by presence of diabetes at enrollment [yes/no] and use of thiazolidinediones (TZDs) or vitamin E at baseline [yes/no]. Biopsy-confirmed NASH will be determined by central reading of liver histology at Screening, and all subsequent histology assessments will be performed centrally in a blinded fashion. At Month 18 or early termination, biopsy slides will be paired-read with the screening biopsy in a blinded fashion to minimize temporal bias of the Month 18 biopsy read.

Following Month 18 visits, clinical visits will occur every 6 months for the remaining duration of the study. For any subject who develops an AE of hepatic injury or decompensation, or if cirrhosis is suspected based on criteria other than liver biopsy or clinical outcomes, a liver biopsy is recommended and will be read using Consensus Method except that in a case where a biopsy

was already obtained within 6 months of the suspected liver injury or decompensation event. All deaths and potential liver-related clinical outcomes including clinical events and histological findings of potential disease progression to cirrhosis adjudicated by independent Hepatic Outcome Committee will be used for the End of Study analysis.

[figure not shown]
Investigational product (ie, OCA or placebo) will be taken orally, with water, once daily. Subject safety and laboratory assessments will be evaluated at clinical visits as detailed in the protocol.

With the exception of liver transplant, if a subject experiences a suspected or confirmed clinical outcome event, he or she should continue the regular visit schedule and continue taking investigational product as long as none of the criteria for discontinuation outlined in the protocol have been met. Subjects who discontinue investigational product due to Investigator or Sponsor decision are expected to be followed through to study closure (or at the discretion of the Sponsor).

Details of study procedures and assessments are described in the protocol.

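### Protocol 8.2.1 allows dosing after an outcome event on Investigator judgement alone, contrary to the Table 4 stop for hepatic decompensation

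*Protocol*

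**What the plan says.** The rule on study drug after a suspected or confirmed clinical outcomes event appears in four places. All four except liver transplant; they differ in the condition for staying on drug.

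- Protocol Synopsis, Study Design: "as long as the subject has not met any of the criteria for discontinuation outlined in the protocol".
- Protocol 7.1: "as long as the subject has not met any of the criteria for discontinuation outlined in" Section 7.7.
- SAP 2.2.1: "as long as none of the criteria for discontinuation outlined in the protocol have been met".
- Protocol 8.2.1: "continue taking investigational product as long as the Investigator assesses it as safe".

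The 8.2.1 sentence does not mention Section 7.7 or Table 4. Later in the same paragraph, under a general qualifier, the protocol adds that "subjects should be strongly encouraged to both stay on investigational product and remain in the study until study termination".

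Table 4 lists potential hepatic decompensation, or progression to Child-Pugh B or C (score 7 or more), under dose discontinuation without rechallenge. The subject stays in follow-up, but "the subject should not be rechallenged. Monitor closely for clinical outcomes according to protocol assessments". Section 7.4.2.1 repeats the stop at a Child-Pugh score of 7 or more for subjects who meet the criteria for progression to cirrhosis.

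**The concern.** Section 8.2.1 does more than leave out a cross-reference. It sets its own test for whether to keep dosing after an outcome event, and that test is the Investigator's opinion. Table 4 does not depend on that opinion: once decompensation is suspected or Child-Pugh B or C is reached, drug stops. A site that looks up what to do after, say, a variceal bleed can find two different answers.

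What is at stake is subject safety. Section 5.5 reports nine cases of hepatic decompensation as SUSARs in NASH trials, one of them fatal. It says that serious hepatic events were more frequent on OCA 25 mg than on OCA 10 mg or placebo, and that the drug has not been studied in NASH subjects with decompensated cirrhosis. A subject kept on drug under 8.2.1 would be in that unstudied group, and the exposure and safety data after the event would reflect dosing that the protocol elsewhere rules out.

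**Working it through.** No arithmetic beyond counting applies. The check sets the statements of the rule side by side and compares the Table 4 stops with the composite components.

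**1. The condition for continuing**

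| Place | Limited by discontinuation criteria? | Investigator judgement is the test? |
|---|---|---|
| Protocol Synopsis | Yes | No |
| Protocol 7.1 | Yes (Section 7.7) | No |
| SAP 2.2.1 | Yes | No |
| Protocol 8.2.1 | No | Yes |

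The limit is in 3 of 4 statements. The SAP does not instruct sites, so within the protocol alone the count is 2 of 3.

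**2. Which Table 4 discontinuation rows concern outcome events**

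There are two: liver transplantation, and potential decompensation or Child-Pugh B or C. Section 8.2.1 excepts the first and not the second, so it covers 1 of 2.

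**3. Which composite components fall under the uncovered row**

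Protocol 16.4.1 lists eight component types: death, MELD of 15 or more, liver transplant, variceal bleed, hepatic encephalopathy, spontaneous bacterial peritonitis, ascites, and progression to cirrhosis. Without death and transplant, 8 − 2 = 6 remain.

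- Footnote e to Table 4 reads "Clinically evident complications of portal hypertension (eg, ascites, variceal hemorrhage, hepatic encephalopathy"). It names three of the six: ascites, variceal bleed and encephalopathy. The list is given as examples, so 3 of 6 is a minimum.
- Section 5.5, describing the reported decompensation cases, also lists MELD of 15 or more and spontaneous bacterial peritonitis. If Table 4 is read that broadly, the count is 3 + 2 = 5 of 6. That reading is an assumption, because Table 4 does not name these two.
- The sixth, progression to cirrhosis, requires a stop only with Child-Pugh B or C. With Child-Pugh A, Table 4 reduces the dose to at most 10 mg.

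**4. The footnote marker**

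In the text as extracted, the decompensation row carries marker c, but footnote c is a laboratory list: "ALT, ALP, direct or total bilirubin, or INR". Footnote e is attached to no other row, so it is taken here as the intended one. The mismatch may come from the PDF reading and is not itself raised as a fault. The conflict does not depend on it, because the row names decompensation and Child-Pugh B or C directly.

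**5. Effect on the analysis**

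Dosing after a confirmed first event cannot change the time to that event. SAP 2.3.2.1 counts events after discontinuation, interruption or dose adjustment under a treatment-policy strategy. The primary analysis, alpha and power stay as planned.

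**The case against.** The strongest reply is that Table 4 plainly governs. Section 8.2, immediately before 8.2.1, sends the reader to Sections 7.4 and 7.7 for decompensation and cirrhosis, and presents 8.2.1 to 8.2.3 as covering other reasons. Sections 7.4, 7.7 and 9.1 also point to the Section 7.7 criteria or Table 4. Sections 7.4.2, 7.4.2.1 and 7.4.3 and the visit procedures in 9.9 describe discontinuation at Child-Pugh B or C. Section 15.1.6.1 requires prompt contact with the Medical Monitor. A site would have to overlook all of this and rely on one sentence. It can also be said that both texts can be obeyed together, by stopping when either Table 4 or the Investigator says so.

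Much of this stands. It shows what the sponsor intended and lowers the practical risk. The encouragement to stay on drug is general retention language and adds little to the concern.

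It does not remove the conflict. Despite its heading, 8.2.1 speaks about outcome events specifically. It tells the subject to continue for as long as one condition holds and presents that condition as sufficient. A reader can obey both texts only by adding a limit that the sentence leaves out and that the other three statements include.

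**Conclusion.** The concern holds. Section 8.2.1 is wrong as written: for decompensation or Child-Pugh B or C it permits, on Investigator judgement, what Table 4 prohibits. It is one looser sentence against a consistent body of other text, not the sole operative rule.

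The firm figures are that 1 of 4 statements lacks the limit, 1 of the 2 relevant Table 4 stops is not excepted, and at least 3 of 6 component types are affected. The last figure rests on reading footnote e as belonging to the decompensation row. The number of subjects who could be affected cannot be derived from the documents, and no misdosing is shown. This is a safety-relevant inconsistency that should be corrected. It does not threaten the trial's inference.

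**What to change.** End the 8.2.1 sentence with the Section 7.1 condition, "as long as the subject has not met any of the criteria for discontinuation outlined in" Section 7.7 (Table 4), and add that the Investigator must also judge continued dosing to be safe. This keeps clinical judgement as a further reason to stop and no longer as the only test.

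Make the change at the next amendment and tell sites by letter, so that they do not rely on the present wording in the meantime. The cost is one sentence and one letter. The event count, alpha, power and analysis do not change.

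At the same amendment, confirm in the source document that the decompensation row of Table 4 carries footnote e.
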